## Measures

All participants will complete the Pittsburgh Sleep Quality Index, Hospital Anxiety and Depression Scale, and Fatigue Symptom Inventory after consent (i.e., baseline) and after the 6-week intervention (i.e., post-intervention). The post-intervention assessment will also include the Insomnia Severity Index, which will have been administered as part of the screening process. Participants in the intervention group will thus complete two assessments. Participants in the wait-list control group will complete these two assessments (i.e., at baseline and after the 6-week waiting period; i.e., post-waiting) as well as a third assessment after participating in the sessions (i.e., post-intervention). Participants will be sent an e-mail and/or a text message with a link to the follow-up assessment. Participants who have been sent the survey e-mail but have not completed the follow-up survey within 2 days will be contacted up to 3 times to provide any necessary clarifications and/or assistance with completing the survey.

All participants will also complete a 10-item version of the Treatment Perception Questionnaire to assess intervention satisfaction after participating in the sessions (i.e., post-intervention). This validated measure, available in English and Spanish, assesses satisfaction with the intervention, the degree to which participants used the intervention, and the degree to which participants used specific strategies to improve their sleep. Verbal feedback will also be obtained from session participants at the end of each session to identify any terminology that was confusing, or other suggestions for improving the intervention for the future.

Each participant will be sent a \$25 gift card after completing the baseline assessment and a \$75 gift card after completing the post-intervention assessment. Participants randomized to the wait-list group will be provided a \$50 gift card after completing a third assessment after completing an additional assessment after the therapy sessions.

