### SPECIFIC AIMS

**Aim 1: Gather qualitative data from cancer survivors, caregivers, and clinicians to determine the best modality to deliver the new intervention.**

**Aim 2: Develop a new behavioral intervention to reduce cancer-related sleep disturbance in Spanish-speaking cancer survivors.** Hypothesis 1: We hypothesize that we will be able to adapt an existing, written, and manualized behavioral intervention and culturally target this intervention for Spanish-speaking cancer survivors.

**Aim 3: Pilot test the new intervention for feasibility, acceptability, and preliminary efficacy in a sample of N=30 participants.** Hypothesis 2: We hypothesize that participants randomized to receive the new intervention will

report greater pre- to post-treatment reductions in cancer-related sleep disturbance than participants randomized to a wait-list control condition.

**Aim 4: Explore changes in sleep disturbance during the COVID-19 pandemic which may influence future trials of the new intervention.**

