### **Aim 3: Pilot test the new intervention for feasibility, acceptability, and preliminary efficacy in a sample of N=30 participants.**

#### Overview

A randomized, wait-list controlled trial will test the feasibility and acceptability of the new intervention in a sample of 30 breast cancer survivors. Acceptability will be assessed by examining the consent rate, obtaining verbal feedback from the group after each intervention session, and through a 10-item version of the Treatment Perception questionnaire administered to participants at the follow-up assessment. Feasibility will be determined using the number of participants who attend/receive most of the therapy sessions/content. We hypothesize that

≥ 50% of eligible participants approached to participate will sign consent and that ≥ 75% of participants will attend/receive most of the sessions/content. Intervention fidelity will be measured by a trained staff member who will listen to the recorded intervention sessions and note the completion of key intervention elements identified a priori for each session. Preliminary efficacy will be assessed with the Pittsburgh Sleep Quality Index completed before and after completing the intervention.

**Role of PIs:** [name] will oversee all aspects of Aim 3 in close collaboration with [name], who will supervise identification of potentially eligible participants, recruitment of participants, and collection of data. Drs. [name] and [name] will analyze data together. Participants will be recruited only from within Puerto Rico. The intervention sessions will take place via videoconference sessions. The day before each scheduled session a group text message will be sent reminding participants of the next session's date and time and providing a videoconference web link to join the session. It is important for participants to complete a sleep diary each morning noting various characteristics of their sleep the previous night. Because these data are an important topic of discussion during sessions, the group text message will also request participants send a reply text message with a photograph of their sleep diary.

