### **Eligibility Screening and Recruitment**

Eligible breast cancer survivors (n=30) will: a) be ≥ 18 years old, b) be able to speak and read Spanish, c) have no documented or observable disabilities that would interfere with study participation, d) have completed primary treatment for breast cancer (e.g., surgery, chemotherapy, radiation), e) report clinically significant sleep disturbance (i.e., ≥ 8 on the Insomnia Severity Index), f) be at low risk of other sleep disorders that are not amenable to treatment with cognitive-behavioral therapy using the Duke Structured Interview for Sleep Disorders, and g) have access to the Internet and a digital device (e.g., smartphone) capable of using videoconference software.

Potential cancer survivor participants will be recruited from clinics, cancer support groups in the Southern Puerto Rico area, using flyers, postings to online bulletin boards, and via referral from individuals who have heard of the study. All potentially eligible survivors will be approached in a HIPAA-compliant manner by a trained research team member in person and/or via telephone. Those who are approached through medical clinics will be identified in consultation with the medical team. Those who are approached through cancer support groups will be identified in consultation with the cancer support group leader(s). Those who learn of the study via flyers, online postings, or referrals will contact the study team via the telephone number provided to them.

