Eligibility will be confirmed through a brief questioning of the potential participant. Participants who meet all eligibility criteria will be provided with an explanation of the study and the opportunity to ask questions. Eligible and interested patients will be asked for an e-mail address and sent an e-mail invitation to a web link to an electronic informed consent form. Participants may also opt to be sent the invitation via a text message. Participants who follow the link and sign consent electronically will then be asked to complete a baseline assessment via the Internet. Participants will then be randomized to either the intervention or a wait-list control condition. After completing the 6-week waiting period, wait-list control group participants will be asked to complete the assessment via the Internet again before being invited to participate in an intervention group. Participants who have been sent the e-mail invitation but have not completed the informed consent form and/or baseline survey within 2 days will be contacted up to 3 times to provide any necessary clarifications and/or assistance with completing the consent form and/or survey.

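### The only pre-treatment ISI is the screening score used for selection; adding the ISI to the baseline web survey is a cheap improvement, although no planned between-arm comparison is biased

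*Combined protocol and SAP*

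**What the plan says.** Aim 3, Measures, lists three instruments for the survey that follows consent: the PSQI, the HADS and the FSI. The ISI is handled separately: it is added to the post-intervention assessment, and its earlier administration is described by the clause "which will have been administered as part of the screening process".

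Aim 3, Eligibility Screening and Recruitment, requires that participants "report clinically significant sleep disturbance", defined as an ISI of 8 or more. It adds: "Eligibility will be confirmed through a brief questioning of the potential participant". Electronic consent, the web baseline survey and randomization follow, in that order.

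Aim 3, Data Analysis, names the ISI as one of three measures of sleep disturbance. It is used as a continuous score and, in secondary analyses, as a category with the same cut of 8. The main purpose of the efficacy analysis is the between-group Cohen's d at follow-up. Mixed models are planned, but their terms are not given. Hypothesis 2 (Specific Aims) expects the intervention arm to "report greater pre- to post-treatment reductions in cancer-related sleep disturbance" compared with the wait-list arm.

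**The concern.** No ISI is scheduled between screening and the end of the six weeks. If a pre-treatment ISI is used at all, it has to be the score on which participants were selected. A score that must exceed a cut-off to be observed is, on average, above the participant's usual level, so a second measurement tends to be lower without any treatment. Selection also narrows the spread of the score, which weakens it as a predictor of follow-up.

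Three things are at stake:

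- **Within-arm change.** Some of any fall in ISI from screening to follow-up would be an artefact. This matters most for the wait-list arm's third assessment, after its own sessions, which has no concurrent control.
- **The category at 8.** Everyone meets it at screening by the entry rule, so its prevalence can only stay level or fall.
- **Precision.** With 30 participants, a better baseline covariate is worth having if it costs almost nothing.

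The screening ISI may also have been given orally, or some time before the web survey. The documents state neither the mode nor the interval, so these are possibilities only.

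**Working it through.** **Inputs from the documents.** N = 30; entry at ISI of 8 or more; ISI at screening and follow-up only; web baseline survey before randomization. The plan gives no figure on this point to reproduce.

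**Assumptions.** Equal allocation, 15 per arm (no ratio is stated). Normal scores. The wait-list arm's six-week survey includes the ISI; the Measures section does not settle this, and it should be confirmed separately.

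**Model A: all pairs of scores equally correlated.** Screened-pool mean 8, 11 or 14; SD 4.5 or 6; correlation ρ of 0.6, 0.7, 0.8 or 0.9, giving 24 scenarios. The cut-off is 7.5 on a continuous scale.

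- a = (7.5 − mean)/SD; λ = φ(a)/[1 − Φ(a)]; δ = λ(λ − a)
- Expected drop with no treatment effect = (1 − ρ) × SD × λ
- Correlation of screening score with follow-up = ρ√(1 − δ)/√(1 − ρ²δ)
- Correlation of a fresh baseline with follow-up = (ρ − ρ²δ)/(1 − ρ²δ)

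Worked case, mean 11, SD 6, ρ = 0.7:

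- a = −3.5/6 = −0.583, λ = 0.467, δ = 0.467 × 1.051 = 0.491
- Drop = 0.3 × 6 × 0.467 = 0.84 points
- Screening correlation = 0.7 × √0.509/√0.759 = 0.573
- Fresh-baseline correlation = (0.700 − 0.241)/0.759 = 0.605
- Adjusted variance ratio, screening to fresh = (1 − 0.573²)/(1 − 0.605²) = 1.06, so the SE ratio is 1.03

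Over the 24 scenarios:

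- The spurious drop is 0.07 points (mean 14, SD 4.5, ρ = 0.9) to 1.79 points (mean 8, SD 6, ρ = 0.6), or 0.02 to 0.34 of the follow-up SD. From a fresh baseline it is 0 in this model.
- With no effect, 3% to 28% would be below 8 at follow-up.
- The screening score has the lower correlation with follow-up in every scenario. Adjusted variance is 1% to 8% higher, so the SE is about 1% to 4% higher.

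**Model B: fresh baseline closer to follow-up.** Correlations: screening–baseline 0.75, baseline–follow-up 0.65, screening–follow-up 0.60. The cut-off c is in SDs from the pool mean. The drop is (1 − 0.60)λ from screening and (0.75 − 0.60)λ from a fresh baseline, in pool SDs.

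| c | λ | Drop from screening | Drop from fresh baseline | R², screening | R², fresh | SE ratio |
|---|---|---|---|---|---|---|
| −0.5 | 0.509 | 0.20 | 0.08 | 0.215 | 0.303 | √(0.785/0.697) = 1.06 |
| 0 | 0.798 | 0.32 | 0.12 | 0.170 | 0.268 | √(0.830/0.732) = 1.06 |
| 0.5 | 1.141 | 0.46 | 0.17 | 0.131 | 0.238 | √(0.869/0.762) = 1.07 |

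Read the other way, a fresh baseline cuts the SE by about 6%.

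**Check on between-arm bias.** 10,000 simulated trials, 15 per arm, mean 11, SD 6, ρ = 0.7:

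- No effect: mean change from screening is −0.84 in each arm; the between-arm difference is 0.00.
- True effect of −3 points: estimates are −3.02 (follow-up only), −3.04 (change from screening), −3.04 (adjusted for screening) and −3.02 (adjusted for a fresh baseline).
- With no effect, the SE of the adjusted difference is 1.60 with screening and 1.54 with a fresh baseline.

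**The case against.** A reader might infer that Hypothesis 2 itself is compromised, because it speaks of reductions from before to after treatment. The documents do not support that. The hypothesis compares those reductions with the wait-list arm's, selection comes before randomization, and the artefact is therefore equal in expectation in both arms and cancels. The stated main quantity, d at follow-up, uses no baseline value at all. This objection stands in full.

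Other points on that side also carry weight:

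- No sentence says that the screening ISI will serve as the pre-treatment value, or that the mixed model will adjust for it. Both are inferences from the schedule.
- No within-arm ISI test is planned. The Aim 3 Overview ties preliminary efficacy to the PSQI before and after the intervention, and the PSQI has a proper baseline. The ISI is one measure of a secondary outcome in a feasibility pilot.
- The precision gain is small. A re-test soon after screening may largely repeat the first answers and make it smaller.
- The artefact could be negligible: the low end of the range is 0.02 SD, and the top case (0.46 SD) needs a screened pool whose mean lies below the entry cut-off.

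What remains is that the ISI is a named efficacy measure without a baseline free of the entry rule, that within-arm ISI changes are easily reported and misread, and that the remedy is nearly free.

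**Conclusion.** The point holds as a cheap improvement, not as a flaw in the controlled comparison. Change in ISI from screening within an arm, and the within-arm fall in the category at 8 or above, cannot be read as treatment effect. About 0.02 to 0.46 SD per arm could be regression to the mean. The lower part of that range is in follow-up SDs (Model A) and the upper part in screened-pool SDs (Model B). The screening score is a weaker covariate: the SE is about 1% to 4% larger with equal correlations and 6% to 7% larger if a fresh baseline correlates more closely with follow-up. All these sizes rest on assumed means, SDs and correlations; only the direction follows from the design.

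A fresh baseline removes the artefact entirely only under equal correlations. In Model B, 0.08 to 0.17 SD remains, so caution about within-arm change is needed either way.

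**What to change.** In Aim 3, Measures, add the ISI to the web survey taken after consent and before randomization. In Aim 3, Data Analysis, state that this value is the ISI baseline in the mixed model and that the screening ISI is used for eligibility only. Add a sentence that change from the screening ISI within an arm, including the wait-list arm's change to its third assessment and any fall below 8, will not be interpreted as a treatment effect.

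The cost is that participants complete one short questionnaire twice before randomization. No visit or staff time is added. If baseline data have already been collected, report ISI contrasts between arms only and give within-arm ISI change without interpreting it as an effect.

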## Data Analysis

The primary outcomes for this intervention are acceptability and feasibility. The study will be deemed acceptable if  $\geq 50\%$  of eligible cancer survivors who are approached agree to participate and  $> 50\%$  of intervention group participants report that, on average, they agree with positive statements about the intervention (i.e., report an average score of  $\geq 3$  on a scale of 0 to 4). The study will be deemed feasible if  $\geq 75\%$  of the intervention group participants attend at least half of the educational components of the intervention. This will be operationalized as having attended at least half of the sessions. The secondary outcome is sleep disturbance, and efficacy data will be examined at the conclusion of the intervention. Sleep disturbance will be operationalized by scores on the Pittsburgh Sleep Quality Index, sleep efficiency (the percentage of time spent in bed that is spent asleep), and the Insomnia Severity Index. The primary efficacy outcome will be the continuous measures of sleep disturbance. For secondary efficacy analyses, participants will be categorized as having sleep disturbance if 1) their Pittsburgh Sleep Quality Index score is  $\geq 5$  (for subjectively-measured sleep disturbance), 2) if their sleep efficiency is  $<85\%$  (for objectively-measured sleep disturbance), and 3) if their Insomnia Severity Index score is  $\geq 8$ . Although statistical significance will be evaluated, the primary purpose is to compute the effect size at follow-up (Cohen's  $d$ ; difference between groups divided by the pooled standard deviation). Intent-to-treat analyses will be conducted, such that all participants who are randomized will be asked to provide follow-up data at the end of the intervention period regardless of the level of use of the intervention. Participants who do not provide complete follow-up data will not need to have data imputed due to the use of mixed model analyses.

**Aim 4: Explore changes in sleep disturbance during the COVID-19 pandemic which may influence future trials of the new intervention.**

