## Eligibility Screening and Recruitment

Eligible breast cancer survivors (n=40) will: a) be  $\geq$  18 years old, b) be able to speak and read Spanish, c) have no documented or observable disabilities that would interfere with study participation, d) have completed primary treatment for cancer (e.g., surgery, chemotherapy, radiation), e) have access to the Internet and a digital device (e.g., smartphone) capable of using videoconference software, and f) report clinically significant sleep disturbance (i.e.,  $\geq$  8 on the Insomnia Severity Index).

The study team will post a study flyer with study team contact information to online bulletin boards, in community oncology clinics, and at meeting places for support groups. Potentially eligible survivors will contact the study team. Study team members will describe the study procedures, offer an opportunity for the individual to ask questions, determine eligibility, review consent information, and solicit verbal informed consent from eligible and interested individuals. Verbally consented participants will be sent a PDF copy of the consent information sheet for their records.

Verbally consented participants will be asked to respond to demographic questions regarding age, relationship status, employment, and education history and medical history questions regarding cancer diagnosis and treatment history. Participants will then be asked for an e-mail address and/or a cellular telephone number to which they can be sent a videoconference session link via unencrypted e-mail and/or text message. Participants will also be asked to provide an address to which they can be sent a gift card after completing the focus group. Participants will then be scheduled for a focus group session. Participants who miss a scheduled focus group or request to reschedule will be scheduled for an upcoming focus group, if available. Each participant will be sent a reminder text message and/or unencrypted e-mail up to 2 days before the scheduled focus group with the videoconference session link.

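### Does the ≥50% consent criterion leave open who counts as approached, what counts as agreeing, and how early refusals are treated?

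*Combined protocol and SAP*

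**What the plan says.** The Aim 3 Data Analysis section makes acceptability and feasibility the primary outcomes. Acceptability has two conditions. At least 50% "of eligible cancer survivors who are approached agree to participate", and more than half of the intervention group must average 3 or higher on the 0-to-4 satisfaction scale.

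The Aim 3 Overview introduces the same measure: "Acceptability will be assessed by examining the consent rate". Its hypothesis is that at least 50% "of eligible participants approached to participate will sign consent".

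The Aim 3 Eligibility Screening and Recruitment section lists clinics, support groups, flyers, online notices and referrals as sources. It continues: "All potentially eligible survivors will be approached in a HIPAA-compliant manner by a trained research team member in person and/or via telephone". It then describes the routes one by one. For clinics, "Those who are approached through medical clinics will be identified in consultation with the medical team", with a parallel sentence for support groups. For the rest, "Those who learn of the study via flyers, online postings, or referrals will contact the study team". On screening it says "Eligibility will be confirmed through a brief questioning of the potential participant". The study is then explained to those who meet every criterion, and those who are interested receive a link to the electronic consent form.

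**The concern.** A pass/fail rule on a primary outcome needs a numerator and a denominator that two analysts would count alike. Three features raise doubt.

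1. **Who was approached.** The general sentence on approach follows a list that includes self-referral sources, so it seems to cover callers. The route-by-route sentences then use *approached* only for clinics and support groups and have the others make contact themselves. The matching Aim 4 section, which recruits by flyer, says only "Potentially eligible survivors will contact the study team". Callers have already shown interest, so their uptake may differ from that of people approached by staff.
2. **What counts as yes.** Agreeing and signing can be separate events here. Interested people are sent a link, and those who have not completed the form within 2 days are contacted up to 3 times. Some who say yes may never sign.
3. **Early refusals.** Eligibility is established by questioning, so a person who declines before that has unknown status. Leaving such people out could make the rate higher than uptake among everyone contacted.

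At stake is whether one half of the acceptability verdict could depend on an unstated counting choice.

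**Working it through.** The plan gives no derivation of the 50% threshold, so there is no figure to reproduce. The only inputs from the documents are the planned 30 participants and the 50% threshold. All other counts below are assumptions chosen to see how far each choice could matter.

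**Limit for a pass.** If exactly 30 sign, 30/N ≥ 0.50 requires N ≤ 60.

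**Self-referred callers.** Let S be eligible callers, x the callers who sign, and D the eligible survivors approached by staff, of whom 30 − x sign.

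- Callers counted: rate = 30/(S + D), a pass if D ≤ 60 − S.
- Callers not counted: rate = (30 − x)/D, a pass if D ≤ 60 − 2x.
- The two limits differ by |2x − S|, which is zero when callers sign at exactly 50%.

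| S, x (caller uptake) | D | Callers counted | Not counted | Verdicts |
|---|---|---|---|---|
| 11, 10 (91%) | 30 | 30/41 = 73% | 20/30 = 67% | both pass |
| 11, 10 (91%) | 45 | 30/56 = 54% | 20/45 = 44% | differ |
| 11, 10 (91%) | 60 | 30/71 = 42% | 20/60 = 33% | both fail |
| 25, 10 (40%) | 38 | 30/63 = 48% | 20/38 = 53% | differ, reversed |

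For S = 11 and x = 10 the limits are D ≤ 49 and D ≤ 40, so the verdicts differ only for D from 41 to 49. For S = 20 and x = 10 both limits are D ≤ 40, and the verdicts never differ. For S = 25 and x = 10 the limits are 35 and 40, and the direction reverses. Neither reading is always the more lenient.

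**Numerator.** Suppose 33 agree and 30 sign. Then 33/N ≥ 0.50 for N ≤ 66, and 30/N ≥ 0.50 for N ≤ 60, so the verdicts differ only for N from 61 to 66. At N = 64 the rates are 33/64 = 52% and 30/64 = 47%. At N = 50 they are 66% and 60%, both passes. This matters only if the two wordings name different measures. The Overview calls the measure a consent rate and gives signing as the event. The Data Analysis section repeats the same threshold and the same eligible-and-approached denominator. Nothing in Aim 3 makes verbal agreement a recorded event.

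**Early refusals.** Let E be confirmed eligible survivors and R the refusers who would have been eligible. Adding R to the denominator changes a pass to a fail only if E + R > 60. With E = 40 and R = 20 the rate falls from 30/40 = 75% to 30/60 = 50%, still a pass. With E = 55, R = 5 gives 30/60 = 50% and R = 6 gives 30/61 = 49%. But both sections restrict the denominator to eligible people, and eligibility is confirmed by questioning before the study is explained. Someone who declines earlier is not known to be eligible and has not yet had the study explained, so does not enter.

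**Scale.** At the threshold itself, 30 of 60, the exact 95% interval is 36.8% to 63.2%. The 9-point gap in the D = 45 row (53.6% − 44.4%, rounded) is smaller than either arm of that interval.

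**The case for a change.** The strongest case for acting is that the outcome is primary, the rule is pass/fail, and the recruitment section uses *approached* in two ways within one paragraph while the criterion does not choose between them. Under plausible assumed counts the verdict can cross 50%. Recruitment source and early refusals may also be hard to reconstruct if nobody logs them at the time, and a clarifying sentence would cost almost nothing.

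Part of this stands. The status of callers is not stated, and a sentence on it would be harmless. The rest is weaker. The general sentence on approach covers all potentially eligible survivors, and the sentences after it describe how each route works without saying that callers are not approached. The Overview speaks of being approached to participate, and an eligible caller gets the same explanation and the same consent link as anyone else. The Aim 4 wording belongs to a focus-group study with verbal consent and no consent-rate criterion, so it does not define the Aim 3 term. Reporting by route and listing pre-screening refusals is good practice in any pilot, but the rate can be computed without it, and silence about a log does not show that none is kept.

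**Conclusion.** This is a gap in detail that analysts can fill sensibly, together with a loose paraphrase. The numerator is signed consent and the denominator is survivors confirmed eligible; the text supports both. Whether callers are counted is open, but uptake among all eligible survivors offered participation and uptake among those approached by staff are both sound measures, and a report need only say which was used.

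The possible effect is confined to a band of counts near 50%: D from 41 to 49 in the example most favourable to the concern, which assumes 91% caller uptake. It vanishes at 50% caller uptake and changes sign below that. These figures rest on exactly 30 people signing and on assumed numbers of callers. The consequences are also limited. Acceptability requires the satisfaction condition as well, verbal feedback is collected, and the documents attach no go/no-go decision to the result. The threshold and the denominator are reasonable as they stand, and no change to the plan is needed.

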### **Intervention Procedure**

Participants will be randomized to one of two arms: 1) the Spanish-language cancer-related sleep disturbance intervention or 2) wait-list control condition. Participants in the intervention group will be asked to attend videoconference group therapy sessions to be scheduled by the study team. These groups will be comprised of up to 10 participants per group and will meet weekly for 6 weeks. The groups will provide patients instruction in the following components of cognitive-behavioral therapy for cancer-related sleep disturbance:

- Sleep Education: education regarding sleep
- Sleep Hygiene: recommendations to ensure the bed and bedroom are conducive to sleep
- Sleep Restriction: consolidate time spent in bed to the actual sleep time and retrain the sleep-wake cycle

- Stimulus control: limiting non-sleep activities in bed, such as watching television, using mobile devices and re-associate the bed/bedroom with sleep
- Relapse Prevention: strategies to continue improvements made during the intervention
- Cognitive Restructuring: helping patients avoid automatic negative thoughts regarding difficulty sleeping that may make it more difficult for patients to fall asleep or stay asleep

Participants randomized to the wait-list control condition will wait 6 weeks, complete a follow-up assessment via the Internet, and then be provided access to videoconference intervention group sessions identical to those provided to intervention group participants.

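### The feasibility rule counts attendance at half of the six sessions, but the stated hypothesis requires most of them, so the trial can be called feasible while its hypothesis fails

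*Combined protocol and SAP*

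**What the plan says.** All of the text is in the current Aim 3 sections of the combined protocol and SAP.

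- **Status of the outcome (Data Analysis):** "The primary outcomes for this intervention are acceptability and feasibility".
- **Definition (Overview):** "Feasibility will be determined using the number of participants who attend/receive most of the therapy sessions/content".
- **Hypothesis (Overview):** at least 75% "of participants will attend/receive most of the sessions/content".
- **Decision rule (Data Analysis):** the study is feasible if at least 75% "of the intervention group participants attend at least half of the educational components of the intervention". The next sentence makes this concrete: "This will be operationalized as having attended at least half of the sessions".
- **Number of sessions (Intervention Procedure):** the groups "will meet weekly for 6 weeks".

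No section defines *most* as at least half. The operationalising sentence in Data Analysis turns educational components into sessions; it does not mention *most*.

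**The concern.** The 75% proportion is the same in both sections, but what a participant must do to count towards it is not. The difference has an effect because the number of sessions is even. With an odd number, at least half and more than half would be the same count; with six, they are 3 and 4.

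The two sections also differ in what is counted and in whom. The Overview accepts content attended or received and speaks of participants. Data Analysis counts attendance only and names the intervention group.

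A feasible verdict on a primary outcome is likely to be read as confirming the stated hypothesis, although the rule behind it sets an easier attendance threshold. If the mismatch comes to light only after attendance is known, whoever resolves it will know which reading passes.

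**Working it through.** The plan gives no operating characteristics for the feasibility rule, so there is no stated figure to reproduce.

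**Inputs from the protocol.** Six sessions (Intervention Procedure); a 75% bar (Overview and Data Analysis); 30 participants in total (Overview).

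**Assumptions.** 15 in the intervention arm, since the allocation ratio is not stated; *most* read as more than half; attendance only, with no credit for content received in another way; participants independent of one another.

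**Step 1: thresholds per participant.** At least half of 6 is 3 or more. More than half of 6 is 4 or more. The readings differ only for someone with exactly 3 sessions (3/6 = 50%).

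**Step 2: pass mark for the arm.** 0.75 × 15 = 11.25, so 12 are needed (12/15 = 80.0%; 11/15 = 73.3%).

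**Step 3: worked cases.**

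| Attend 4+ | Attend exactly 3 | Attend fewer | Data Analysis rule | Overview hypothesis |
|---|---|---|---|---|
| 11 | 1 | 3 | 12/15 = 80%, feasible | 11/15 = 73%, not met |
| 9 | 3 | 3 | 12/15 = 80%, feasible | 9/15 = 60%, not met |

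**Step 4: how often the two would disagree.** Let p be the chance of attending any one session and r the within-person correlation. Sessions attended follow Binomial(6, p) when r = 0. Otherwise they follow a beta-binomial with a = p(1−r)/r and b = (1−p)(1−r)/r. Anyone with 4 or more also has 3 or more, so

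P(feasible, hypothesis fails) = P(Bin(15, share with 3+) ≥ 12) − P(Bin(15, share with 4+) ≥ 12).

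Example, p = 0.70 and r = 0: the shares are 0.930 and 0.744, the two tail probabilities are 0.982 and 0.441, and the difference is 0.541.

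| p | r = 0 | r = 0.2 | r = 0.5 |
|---|---|---|---|
| 0.60 | 0.725 − 0.039 = 69% | 0.380 − 0.042 = 34% | 0.188 − 0.053 = 13% |
| 0.70 | 0.982 − 0.441 = 54% | 0.778 − 0.278 = 50% | 0.493 − 0.238 = 25% |
| 0.75 | 0.998 − 0.759 = 24% | 0.906 − 0.505 = 40% | 0.671 − 0.410 = 26% |
| 0.80 | 1.000 − 0.946 = 5% | 0.971 − 0.741 = 23% | 0.825 − 0.617 = 21% |
| 0.90 | 0% | 0.999 − 0.983 = 2% | 0.984 − 0.944 = 4% |

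Differences were taken before rounding.

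**Step 5: precision.** Exact (Clopper-Pearson) 95% intervals are 0.519 to 0.957 for 12/15, 0.449 to 0.922 for 11/15 and 0.323 to 0.837 for 9/15. The intervals overlap heavily, so the pass or fail label rests on very few people.

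**The case against.** The best defence is that Data Analysis contains the only operational rule. It gives the cut-off, the denominator and the attendance threshold, and it can be read as making a loose word in the Overview concrete. On that reading the bar is already prespecified and only the hypothesis sentence is badly worded. It is true that the working rule is clear. But the text does not say that the rule defines *most*, and 3 of 6 is not most. The rule can still return feasible when the hypothesis, as written, is not met.

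A second point is that the Overview also credits content received. Someone who attended few sessions might qualify there and fail in Data Analysis, so the mismatch could also run the other way. This stands, and it limits Step 4 to an attendance-only reading. It does not remove the problem: one participant with exactly 3 sessions and no other content is enough for the results to diverge in the direction described.

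A third point is that the probabilities depend on assumed attendance, correlation and arm size. That also stands. The 69% needs 60% attendance and full independence between sessions, which is hard to defend for repeated attendance by the same person. At a correlation of 0.5 no tabulated value exceeds 26%.

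Finally, this is a 30-person pilot, and nothing ties the verdict to a formal decision to proceed. That limits the consequence, but feasibility is still a primary outcome.

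**Conclusion.** The concern holds. Two current sections set different per-participant thresholds for the same primary outcome, and with six sessions the difference is a real one. The contradiction needs no assumption about attendance, only the ordinary meaning of *most*.

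Its practical size does depend on assumptions. With 15 in the arm, a single participant can separate the two results. The mismatch matters at about 60% to 80% attendance per session and hardly at all at 90%. It should be corrected, but it is a wording fault in a plan whose working rule is otherwise clear.

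**What to change.** Before anyone sees attendance data:

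1. State one threshold, as a number of the six sessions, in both the Aim 3 Overview and Data Analysis. Matching the rule to the hypothesis as written means 4 or more. Rewording the Overview to at least half would also remove the contradiction, but the hypothesis would then have to be restated at 3 or more.
2. Give attend/receive one meaning in both sections, and say whether content received without attending a session counts.
3. Name the intervention group as the denominator in the Overview, as Data Analysis already does.

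For reporting, give the proportion with an exact 95% confidence interval and show the share attending 3 or more beside it, so that readers can see how far the result depends on the threshold. Describing wait-list attendance separately, with the intervention arm kept as the primary set, is optional; its absence is not an error.

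The cost is wording only: no extra participants, visits or data for the intervention arm. The downside of choosing 4 or more is a somewhat harder bar. Under the Step 4 model with r = 0 and 75% attendance, for example, the chance of passing falls from 99.8% to 75.9%.
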